6.0 CRITERIA FOR SUBJECT ELIGIBILITY

6.1 Subject Inclusion Criteria

Patients eligible for inclusion in this study have to meet **all** of the following criteria:

Inclusion criteria:

- Patients must have pathologically confirmed GIST.
- In the Phase Ib portion, must have locally advanced or metastatic GIST and have progressed on imatinib.
- In the Phase II portion, patients must be newly diagnosed or imatinib treatment naïve in the advanced/metastatic setting. Prior adjuvant imatinib therapy is allowed as long as disease

MEMORIAL SLOAN-KETTERING CANCER CENTER IRB PROTOCOL

IRB#: 14-140 A (7)

recurrence was documented ≥ 90 days after last dose of imatinib and imatinib has not yet been restarted.

- Patients must be at least 18 years of age.
- Disease must be measurable by RECIST 1.1.
- ECOG Performance Status 0 or 1.
- Adequate renal, hepatic, and hematologic function as the following: Serum Creatinine ≤ 1.5 mg/dL, Total Serum Bilirubin ≤ 1.5 x upper limit of normal (ULN) unless due to Gilbert's Disease, Serum AST (SGOT) and/or ALT (SGPT) ≤ 2.5 x ULN (or ≤ 5.0 x ULN if considered due to tumor), ANC $\geq 1500/\text{mm}^3$, Platelets $\geq 100,000/\text{mm}^3$, and hemoglobin $\geq 10\text{g/dL}$.
- Patients of childbearing potential must have a negative blood pregnancy test within 14 days of treatment. Patients must agree to use a reliable barrier method of birth control during and for 3 months following the last dose of study drug.
- Patient must have adequate cardiac function (left ventricular ejection fraction (LVEF) $\geq 50\%$ as determined by a multigated acquisition (MUGA) scan or echocardiogram; and QTc interval ≤ 480 ms by Fridericia's formula (QTcF).
- Patient must be able to take oral medications.
- Patients must sign an informed consent document.

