
Key for Table 10:
 
Schedule of Phase 2
 
Evaluations
	
X: Imatinib: Dose as assigned; PO once daily
 
Y: BGJ398: Dose as assigned; PO once daily the treatment schedule will be determined by the phase 1b portion of the study
 
a: Comp- Albumin, alkaline phosphatase, total bilirubin, bicarbonate, BUN, calcium, chloride, creatinine, glucose, potassium, total protein, SGOT [AST], SGPT [ALT], sodium. In addition, LDH, phosphorus, magnesium, creatine kinase (CK), amylase, lipase.
 
b: Blood pregnancy test (women of childbearing potential) once at baseline; blood or urine pregnancy test at the discretion of the investigator while on study.
 
c: Off-study evaluation performed 4 weeks after removal from study.
 
d: Day 1 of every cycle while on study. At the investigator's discretion, patients can return for RN/MD visits and get evaluated every 8 or 12 weeks after cycle 4. Laboratory assessments and EKG assessments between MD/RN visits can be performed locally with results sent to the study site
 
e: TTE or MUGA will be performed once at week 16 as well as any time felt to be necessary by the investigator. Modalities should remain consistent whenever feasible.
 
f: Scans should be performed every 8 weeks x 4 starting after 2 cycles (e.g. C3D1, C5D1, C7D1, C9D1), then every 12 weeks (C12D1, C15D1, etc). Radiologic documentation must be provided for patients removed from study for progressive disease within 28 days of clinical assessment of progression if no scan was performed within 28 days of the time of that assessment.
 
g: FDG PET scan will be performed at baseline (pre-treatment) and during week 3 of combination therapy (C1D21).
 
h: Tumor biopsy will be performed pre-treatment, after week 1 (C1D8) of therapy, and at disease progression for patients who have consented for research biopsies including the first twenty mandatory patients and any subsequent voluntary patients. A +/- 4 day window will be provided for the biopsies to account for scheduling.
 
i: Four research blood 4-8mL vials will be obtained at baseline (week -2), two weeks after the single agent imatinib lead in (C1D1 of combination therapy), week 3 (C1D15), week 5 (C2D1). At least one tube at those timepoints will be used for imatinib trough levels, and two tubes will be used for correlative analyses. Imatinib levels will be prioritized.
 
j: Two research blood 4-8mL vials for correlative analyses will be obtained at the time of progression.
 
k: At eye exams the follow tests should be completed : - slit lamp exam - dilated funduscopic exam with photos - optical coherence tomography testing A follow-up eye exam will occur at week 4 (C1W4) and if the patient develops new or worsening ocular symptoms.
 
l: Study personnel will attempt to contact all evaluable patients every 3 months (± 2 weeks) via telephone, email, etc to assess survival status for up to 3 years.
 
m. CBC and Blood Chemistry performed on Day 1 of each cycle must be resulted prior to treatment
 
All assessments are to be done +/-3 days of the scheduled timepoints unless otherwise noted. Radiologic assessments (CT, PET, TTE) are to be done +/-7 days from the scheduled appointment.

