As imatinib is standard of care for patients with untreated inoperable locally advanced or metastatic GIST, imatinib levels will be tested to ensure that BGJ398 does not affect imatinib serum levels. In Phase Ib, imatinib levels will be tested on C1D2 (24 hour timepoint after the first dose of imatinib&BGJ398) and C1D21 (prior to dosing on that day) on both treatment schedules (A and B). In phase Ib, on schedule B, imatinib level will also be tested on C1D7 (prior to dosing on that day). All participants on the Phase II portion will undergo a 2-week lead in of single agent imatinib in order to establish a steady-state serum imatinib trough level. Imatinib levels will be rechecked during week 3 and week 5 of the combination therapy. We will correlate imatinib levels to primary and secondary outcome measures. Imatinib levels will be stratified into quartiles as done previously [31].

5. **FGF2 Serum Levels:**

Preclinical data suggests that FGF2 levels may correlate with the development of imatinib resistance and may predict response to inhibition with BGJ398. Blood will be collected at baseline (if not on imatinib), after the imatinib lead-in, and during week 3 and 5 of the combination therapy. We will correlate FGF2 levels to our primary and secondary endpoints with the hope of establishing an integral biomarker for BGJ398 and evaluating the penetrance of the FGF pathway in GIST. If collected blood specimen is only adequate for 1 assay, imatinib levels should be prioritized.

Please reference the laboratory manual for instructions on sample labeling and shipping.

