MSKCC-Assigned Participant ID:	
Contents – Sample Information	
Date of Collection: (MM DD YYYY)	Phase I Study Time Point:
	 Cycle 1 Day 2 (24 hours post-first dose / Pre-dose on Day 2)
	 Cycle 1 Day 7 (Pre-dose)
	 Cycle 1 Day 21 (Pre-dose)

Shipment Information		Sender's Contact Information	
Shipping Date		Name	
Shipping Method		Email	
Tracking Number		Telephone	

For MSKCC Use ONLY: Date received at MSKCC: __ / __ / ____ (MM DD YYYY)

MEMORIAL SLOAN-KETTERING CANCER CENTER
IRB PROTOCOL

IRB#: 14-140 A (7)

Phase II: Research Blood Collection

Pharmacokinetic Samples for Imatinib and FGF Serum Levels

Supplies for each sample collection and storage:

- (2-4) 4-8 mL K3-EDTA tubes – provided by site
 - (2) 1.8 mL NUNC 2D coded tubes from Thermo – provided by site
- Reference for tubes: 374502NOV (1D/2D coded tubes) or 374502 (480 tubes/10 bags)

Phase II Collection procedures for Imatinib PKs and FGF Serum Research bloods:

1. Use (4) 4-8mL K3-EDTA tubes for collection at timepoints: Week -2, C1D1, C1D15, C2D1. Use (2) 4-8mL K3-EDTA tubes at the time of progression.
2. All blood samples will be taken by either direct venipuncture or an indwelling catheter inserted in a forearm vein.
3. At specified timepoints, collect a 2mL blood sample in tubes with the specific coagulant K3-EDTA
4. Immediately after blood draw, invert gently several times to ensure mixing of contents. Avoid prolonged blood sample contact with the rubber stopper.
5. Place the tube upright surrounded by ice or cryoblock until centrifugation.
6. Within 30 minutes, centrifuge the sample between 3-5°C for 10 minutes at approximately 2000g.
7. Immediately after centrifugation, 2 aliquots of about 0.5 mL of the collected plasma should be transferred into labeled 1.8 mL NUNC 2D coded tubes from Thermo. At least 0.5 mL of plasma in the first tube and the remaining plasma into the second tube.
8. Immediately freeze the tubes over dry ice (solid carbon dioxide) then keep frozen at $\leq -15^{\circ}\text{C}$.

Labeling and Shipping Instructions:

1. Label samples with MSKCC ID, date of collection, and study time point.
2. Participating sites will ship specimen to MSK. All shipments should be directed to the address listed on the tissue sample shipment form. Samples should be shipped frozen with dry ice by courier so that the package can be tracked appropriately (specifically, Federal Express or UPS).

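### At week -2 the short-sample rule ranks an imatinib assay that must read essentially zero above the only scheduled pre-imatinib circulating FGF2 value

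*Combined protocol and SAP*

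**What the plan says.** Section 10.1.2, Table 11 key, note i begins "Four research blood 4-8mL vials will be obtained at baseline (week -2" and goes on to list C1D1, C1D15 and C2D1. It then allocates the tubes: "At least one tube at those timepoints will be used for imatinib trough levels, and two tubes will be used for correlative analyses". It closes with "Imatinib levels will be prioritized". Week -2 is thus named among the draws that carry an imatinib tube and an imatinib priority.

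Section 10.2.5, item 5 (FGF2 Serum Levels) repeats the priority: "If collected blood specimen is only adequate for 1 assay, imatinib levels should be prioritized". It makes no exception by time point. The same item says why FGF2 is measured: to relate it to the primary and secondary endpoints "with the hope of establishing an integral biomarker for BGJ398". It qualifies the baseline FGF2 sample as one taken off imatinib.

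Section 6.1 admits phase II patients who are imatinib-naive in the advanced setting. It also admits those who recurred at least 90 days after adjuvant imatinib, provided "imatinib has not yet been restarted". Section 6.2 requires the same 90 days before registration. Section 10.2.3 requires every research sample to be drawn before that day's dose.

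**The concern.** A priority rule for scarce samples should protect the measurement that is informative and cannot be obtained at another time. At C1D1, C1D15 and C2D1 the rule does this, because the imatinib trough there bears on whether BGJ398 alters imatinib exposure. At week -2 it does the reverse. The imatinib result is known in advance, while the FGF2 result is not and cannot be collected again once the lead-in starts.

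At stake is the untreated FGF2 value in any patient whose week -2 draw is short. FGF2 is a candidate for selecting patients who might benefit from FGFR inhibition (Section 3.1.6 and item 5), and a selection marker for untreated patients needs a value taken before treatment. The post-lead-in sample is not an obvious substitute. Section 3.1.3 reports that GIST cell lines show activated FGF signalling after three days of imatinib, and the lead-in lasts two weeks.

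**Working it through.** The plan states no figure on this point. The check is a reading of the passages together, with one piece of arithmetic.

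**1. Is the week -2 imatinib level known in advance?** Inputs: minimum time off adjuvant imatinib, 90 days (Sections 6.1 and 6.2); half-lives of about 18 h for imatinib and 40 h for its main metabolite, with 23 h as the upper end of the stated parent range (Section 3.3.3.1).

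- Time off drug: 90 × 24 = 2,160 h.
- Residual fraction = 0.5^(2,160 / half-life).

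| Half-life | Half-lives elapsed | Residual fraction |
|---|---|---|
| 18 h (imatinib) | 2,160 / 18 = 120 | about 8 × 10⁻³⁷ |
| 23 h (longest stated, parent) | 2,160 / 23 = 93.9 | about 5 × 10⁻²⁹ |
| 40 h (metabolite) | 2,160 / 40 = 54 | about 6 × 10⁻¹⁷ |

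The level is effectively nil after adjuvant imatinib and exactly nil in a patient never treated.

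**2. Is there another untreated blood sample for FGF2?** Table 11 has no research blood in the pre-study column. Its draws are week -2, C1D1, C1D15, C2D1 and progression, and all but the first follow the start of imatinib. The FGF2 ELISA item in Section 10.2.5 lists both baseline and the initiation of imatinib, which could suggest two early samples. The calendar and Appendix I provide only one, at week -2.

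**3. Does the imatinib objective need week -2?**

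| Place | Imatinib samples described |
|---|---|
| Section 2.0 | End of lead-in, then weeks 3 and 5 of combination |
| Section 10.2.5, item 1g | One in lead-in, one on combination |
| Section 10.2.5, item 4 | Lead-in steady state, then weeks 3 and 5 |
| Table 11, note i | Week -2, C1D1, C1D15, C2D1 |
| Section 14 | Two in lead-in, two on combination; comparison described as before versus after the lead-in |

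The first three define the comparison from the end-of-lead-in trough onward. Only note i and Section 14 bring in a pre-lead-in sample. A pre-lead-in value is zero and carries no information on the effect of BGJ398 on a steady-state trough, so dropping it costs the comparison nothing.

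**4. How tight is the sample?** Four tubes of 4 to 8 mL give 16 to 32 mL. At least one tube goes to imatinib and two to correlatives, leaving up to 4 − 1 − 2 = 1 unassigned. Appendix I then refers to a 2 mL sample and two stored aliquots of about 0.5 mL: "At least 0.5 mL of plasma in the first tube and the remaining plasma into the second tube". It does not assign either aliquot to an assay.

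**5. Scale.** If a fraction s of week -2 draws suffices for only one assay, the expected loss among 44 patients is 44 × s. The documents give no s. Purely as an assumption, s from 1% to 10% gives 44 × 0.01 = 0.4 to 44 × 0.10 = 4.4 patients. Uninformative imatinib assays at week -2: up to 44, one per planned patient.

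**The case against.** The best reply is that the rule will rarely bite. The sentence in note i that gives imatinib a tube also gives two tubes to correlatives, and four tubes would have to shrink to about one assay's worth before FGF2 was lost. This stands, and it limits the size of the point. It does not remove the point, because the plan foresaw shortage and wrote a rule for it.

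A second reply is that, outside note i and Section 14, no imatinib assay is described at week -2, so nothing competes with FGF2 there. That is fair as a reading of items 1g and 4. It makes this partly an inconsistency over whether a week -2 imatinib sample exists. But note i is the operative calendar, and it names week -2.

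Third, the week -2 assay could detect undeclared imatinib use. The documents never give that as its purpose, and it could still be run on surplus plasma.

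Several stronger readings are tempting and are not supported:

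- That every phase II draw is affected. The progression draw (note j) is for correlatives only.
- That a definite share of patients will lose the value. No rate of short draws is given.
- That all pre-treatment FGF2 information would be lost. Tumour FGF2 and FGFR are also to be assessed by immunohistochemistry, including on pre-treatment biopsies from 20 patients.
- That the two storage tubes in Appendix I commit one to imatinib. The manual does not say so.

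**Conclusion.** The point holds as a small, specific flaw in sample handling. Of the four draws in note i, week -2 is the one where the stated priority is the wrong way round: it protects a result that is effectively zero and exposes the only scheduled untreated circulating FGF2 value.

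The loss is conditional on a short draw, whose frequency the documents do not state and which the planned volume should make uncommon. FGF2 is an exploratory marker with no multiplicity adjustment (Section 14). A reader might infer that the efficacy conclusion or the study of BGJ398's effect on imatinib is at risk. Neither is: the primary endpoint does not use FGF2, and the imatinib comparison starts at the end of the lead-in.

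The conclusion assumes that the week -2 draw precedes the first imatinib dose. The baseline label, the off-imatinib qualifier in item 5 and the pre-dose rule all point that way, although the general ±3-day window does not itself guarantee it. The phase II shipment form in Appendix I was not fully available in the text examined and should be checked for what it lists at week -2.

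**What to change.** 1. In Table 11 note i and Section 10.2.5 item 5, state that at week -2 FGF2 and the other correlatives take priority, and that imatinib is either not assayed or assayed only on surplus plasma. Keep imatinib priority at C1D1, C1D15 and C2D1.
2. In the same edit, align Section 14 with Section 2.0 and with items 1g and 4 of Section 10.2.5. The effect of BGJ398 on imatinib is then the end-of-lead-in trough (C1D1, pre-dose) against the trough on combination (C1D15 and C2D1). Correct the lead-in count of two in Section 14, and settle the on-combination count, which is one in item 1g but two in Section 14, note i and item 4. Without this step, Section 14 would call for a sample that the calendar no longer assays.

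The cost is a sentence in two places and a correction to the sample counts. It changes no treatment, visit or endpoint. Dropping the week -2 assay saves up to 44 assays and gives up an assay check for undeclared imatinib at entry. Running it on surplus plasma keeps most of that check but forgoes most of the saving.

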11.0 TOXICITIES/SIDE EFFECTS

Toxicity grading will be performed in accordance with NCI CTC version 4.03, (http://ctep.cancer.gov/protocolDevelopment/electronic_applications/ctc.htm).

Adverse event (AE) monitoring and reporting is a routine part of every clinical trial. The following list of AEs (Section 11.1) and the characteristics of an observed AE (Section 11.2) will determine whether the event requires expedited reporting in addition to routine reporting.

*All adverse events occurring in $\geq 10\%$ of patients regardless of suspected relationship to treatment

Also reported on Imatinib Mesylate (STI571) trials but with the relationship to Imatinib Mesylate (STI571 still undetermined:

BLOOD AND LYMPHATIC SYSTEM DISORDERS - Disseminated intravascular coagulation; Febrile neutropenia

CARDIAC DISORDERS - Cardiac arrest; Heart failure; Myocardial infarction; Ventricular arrhythmia

ENDOCRINE DISORDERS - Hypothyroidism

EYE DISORDERS - Blurred vision; Conjunctivitis; Papilledema; Photophobia; Watering eyes

GASTROINTESTINAL DISORDERS - Abdominal distension; Duodenal perforation; Esophageal fistula; Esophagitis; Gastritis; Gastrointestinal ulcer⁴; Ileus; Pancreatitis

GENERAL DISORDERS AND ADMINISTRATION SITE CONDITIONS - Flu like symptoms; General disorders and administration site conditions - Other (Guillain-Barre syndrome); Non-cardiac chest pain

HEPATOBIILIARY DISORDERS - Hepatic failure

IMMUNE SYSTEM DISORDERS - Allergic reaction; Autoimmune disorder

MEMORIAL SLOAN-KETTERING CANCER CENTER
IRB PROTOCOL

IRB#: 14-140 A (7)

INVESTIGATIONS - CPK increased; GGT increased; Lipase increased; Weight loss

METABOLISM AND NUTRITION DISORDERS - Hypercalcemia; Hyperglycemia; Hypoalbuminemia; Hypocalcemia; Hypoglycemia; Hypomagnesemia

MUSCULOSKELETAL AND CONNECTIVE TISSUE DISORDERS - Avascular necrosis; Back pain; Bone pain; Generalized muscle weakness; Pain in extremity

NERVOUS SYSTEM DISORDERS - Depressed level of consciousness; Dysgeusia; Encephalopathy; Hydrocephalus; Intracranial hemorrhage; Ischemia cerebrovascular; Peripheral motor neuropathy; Peripheral sensory neuropathy; Seizure; Tremor

PSYCHIATRIC DISORDERS - Anxiety; Confusion; Depression; Insomnia

RENAL AND URINARY DISORDERS - Acute kidney injury; Hematuria; Proteinuria; Renal and urinary disorders - Other (kidney stones)

REPRODUCTIVE SYSTEM AND BREAST DISORDERS - Irregular menstruation

RESPIRATORY, THORACIC AND MEDIASTINAL DISORDERS - Adult respiratory distress syndrome; Allergic rhinitis; Hypoxia; Pharyngolaryngeal pain; Pneumonitis; Pulmonary hypertension; Respiratory hemorrhage⁵; Voice alteration

SKIN AND SUBCUTANEOUS TISSUE DISORDERS - Dry skin; Purpura

VASCULAR DISORDERS - Hypotension; Thromboembolic event; Vasculitis

Note: Imatinib Mesylate (STI571) in combination with other agents could cause an exacerbation of any adverse event currently known to be caused by the other agent, or the combination may result in events never previously associated with either agent.

11.1.2 BGI398

11.1.2.1 Adverse Events, Dose Limiting Toxicities, and Reasons for Discontinuation of BGI398

From 21 December 2009 to 24 September 2013 (data cutoff date), 94 patients received at least one dose of BGI398 in the clinical study CBGI398X2101 and are included in the current safety set. The most common adverse events of all severity grades (CTCAE v.3.0.) suspected to be related to BGI398 (Table 13, below), were hyperphosphatemia (71%), decreased appetite (27%), fatigue (26%), stomatitis (25%), and alopecia (21%). All other adverse events were reported in less than 20% of patients. Overall, most adverse events reported have been mild to moderate in severity. Twenty-six (27.7%) patients experienced at least one grade 3 or 4 event suspected to be related to BGI398.

As of 23 September 2013, four DLTs have been reported in Cycle 1 during dose escalation. One grade 3 event of AST/ALT elevation was reported in the 100mg cohort. In the 125mg cohort, one patient experienced hyperphosphatemia for greater than 14 days despite adequate therapy that resulted in study drug interruption. In the 150mg cohort, one patient each experienced grade 1 corneal toxicity and grade 3 AST/ALT elevations, the latter leading to study treatment interruption and dose reduction. Eleven other DLTs occurred in 6 patients enrolled in the first of two dose expansion cohorts receiving BGI398 125 mg daily, continuous schedule. Five patients experienced

MEMORIAL SLOAN-KETTERING CANCER CENTER
IRB PROTOCOL

IRB#: 14-140 A (7)

hyperphosphatemia that required discontinuation of study drug despite optimal prophylactic treatment with phosphate binders and dietary phosphate restrictions. The sixth patient experienced Grade 3 increases in AST and ALT.

At the time of data cutoff, 0 of 18 patients receiving 125 mg daily 3 weeks on, 1 week off had experienced a DLT.

As of 23 September 2013, among the 94 patients enrolled on the study and available for analysis, 12 patients are still receiving study medication. Of the 82 patients who discontinued treatment, 56 (68%) did so for progression of disease. Ten patients (10.6%) discontinued treatment due to adverse events, including peripheral neuropathy (5mg dose level), pulmonary embolism (10mg dose level), gallbladder removal (20mg), punctate corneal epitheliopathy (60mg dose level), cutaneous lesion growth (100mg dose level) and bilateral retinal detachment (100mg dose level). Neither the retinal detachment nor the punctate corneal epitheliopathy was considered a DLT since they occurred after the first cycle of therapy. Two patients died while on study, both due to disease progression. Twelve patients discontinued due to withdrawal of consent, one patient due to administrative problems, and one patient due to protocol deviation.

As of the data cutoff date, 67 events of hyperphosphatemia among 25 patients were reported at dose levels greater than 60 mg. Twenty of these events led to study drug interruption/dose reduction. Phosphate binding therapy was administered for 38 of these events. The events of hyperphosphatemia were reversible following study treatment interruption and institution of phosphate binding therapy. Most of these events were suspected to be related to study treatment. No clinical adverse events were associated with these events.

Although occasional non-dose-related increases from baseline were observed in ECG interval parameters, including QTc, no adverse events were associated with these ECG findings. No clinically significant findings of QT prolongation have been observed to date. Monitoring of both potential QT-prolongation and left ventricular function are ongoing among the patients enrolled in the expansion cohorts of CBGJ398X2101.

